6. STUDY POPULATION ANALYSES

6.1. Planned Analyses Overview

The study population analyses will be based on the population specified in Section 4.

Table 2 provides an overview of the planned study population analyses with full details of data displays being presented in Appendix 11: List of Data Displays.

Table 2 Overview of Planned Study Population Analyses

Display Type	Data Display's Generated		
	Table	Figure	Listing
Randomization			
Randomization			Y
Subject Disposition			
Study Populations [1]	Y		Y
Subject Disposition [1]	Y		Y
Reasons for Withdrawals [2]	Y		Y
Significant Protocol Deviations [2]	Y		Y
Demography			
Demographics and Baseline Characteristics [2]	Y		Y
Race & Racial Combinations [2]	Y		Y

Medical Condition & Concomitant Medications			
Medical History/Conditions (Obstetrical/Prenatal) ^[2]	Y		Y
Prior/Concomitant Medication ^[3]	Y		Y
Obstetrical Medication, Magnesium Sulfate and Antenatal Corticosteroids ^[3]	Y		Y

NOTES:

1. Listing of subjects the all randomized subjects.
2. Displays generated using the ITT population.
3. Displays generated using the Safety population.

6.2. Disposition of Subjects

Subject status with respect to the infusion of the investigational product (IP) will be summarized in relation to:

- Randomized and not dosed
- Study completion and withdrawal
- IP Discontinuation
- Dose increase
- Re-treatment
- The number and percentage of subjects who complete or withdraw from the study will be summarized by treatment group. Reasons for withdrawal from the study will also be summarized.

The number and percentage of subjects with the above IP status will be reported by treatment group. Reasons for IP discontinuation will be presented. Also, the number and percentage of subjects who are randomized to IP but not dosed will be reported by treatment group.

A completed subject is defined as one who has completed all phases of the study including the post-delivery assessment and neonatal medical review phase. Subjects who receive but who discontinue from IP will not be considered withdrawn from the study and should remain in the study and continue to be followed for efficacy and safety. Also, the number and percentage of subjects withdrawn prior to IP completion and after IP completion will be reported.

Subject disposition data will also be listed and plotted. All disposition summaries will be performed using the all randomized subjects.

6.3. Demographic and Baseline Characteristics

For mothers, continuous variables, such as age (years), weight (kg), height (cm), BMI (kg/m²), gestational age at randomization (weeks/day), contraction frequency, cervical

dilation (cm), cervical length (mm), percentage of women who failed PTL criteria (inclusion criteria #4), fFN (continuous) and other baseline characteristics as needed will be summarized using descriptive statistics by treatment group. Since only year of birth is collected and the month and day of birth are not collected, a mother's age will be calculated using below algorithm.

- The day and month is imputed as '30th June'.
- The age of mother is calculated as the difference of the date of the first study treatment and the date of birth divided by 365.25. For example, if the date of the randomization was at 00:00 am on 20 March 2015 and date of birth was 1987, the age is 27.
- If no inclusion deviation in age requirement, the age is between 12 and 45 year old based on study entry criteria.
- The mother is recorded as an adolescent in CRF if she is adolescent (12 to < 18 years of age), so age will be adjusted. For example, the calculated age is 18.2 but a subject is marked as an adolescent in CRF, a subject's age is to 18.

GA at randomization in weeks/days will be obtained from CRF and will be converted into numeric value as covariate in the statistical analysis of primary and secondary endpoint. Please refer to Appendix 11.6.2 for missing GA at randomization.

The following categorical variables will be summarized by reporting the number and percentage of subjects in each category by treatment group:

- Race
- Ethnicity
- GA at randomization (4 GA strata: $24^{0/7}$ to $25^{6/7}$, $26^{0/7}$ to $27^{6/7}$, $28^{0/7}$ to $30^{6/7}$ and $31^{0/7}$ to $33^{6/7}$)
- Established progesterone use
- Region
- Prior tocolytic use in current episode (Beta-mimetics, Magnesium Sulfate, Calcium channel Blockers, NSAIDs, and Oxytocin receptor antagonists)
- Adolescent (between 12-<18 years) and adult (≥ 18 years) patients.
- fFN (positive or negative)

For fetus, continuous variables, such as estimated weight (g) and AFI results (cm) measured using the 4-quadrant method will be summarized.

Demographic and baseline characteristics data will also be listed. Summaries will be performed using ITT population. For mothers/fetus, demographic and baseline characteristics will be presented in a separate table. Additional baseline characteristics which are not listed above can be included in the final analysis.

Races and racial combinations will be presented in a separate table following GSK race reporting standards.

6.4. Medical Conditions (Current/Past)

The number and percentages of subjects with obstetrical history, and prenatal history will be presented.

In addition, subject level listings of, obstetrical history and prenatal history will be listed.

All summaries will be performed using the Maternal ITT Population.

6.5. Concomitant Medication

Any prior and concomitant medication used during the study will be recorded and coded using World Health Organization Drug Dictionary (WHODRUG), which will be updated whenever available throughout the life of the study. Summary of all medications by treatment group and preferred term will be provided in relation to treatment phase (prior medication or concomitant medication). Prior medications are those started before the first study treatment. Concomitant medications are those taken at any time on or after the day of the first treatment during the study period, including those medications that were started prior to randomization but were continued into the study period. If the medication is taken prior to start of IP and continue into the study period, the medication will be included as both prior and concomitant medication.

For mothers, all prior and concomitant medications will be listed using verbatim and preferred terms. All summaries will be performed using the Maternal Safety Population. In addition, obstetrical medication, magnesium sulphate, and antenatal corticosteroids used during the study will be summarized and listed separately for the Maternal Safety Population.

7. PRIMARY STATISTICAL ANALYSES

7.1. Efficacy Analyses

7.1.1. Overview of Planned Efficacy Analyses

The primary objective of the statistical analysis will be to test the null hypothesis in the ITT Populations that there is no difference between retosiban and atosiban in time to delivery versus the alternative hypothesis that there is a difference.

Table 3 provides an overview of the planned efficacy analyses with full details of data displays being presented in Appendix 11: List of Data Displays.

Table 3 Overview of Planned Efficacy Analyses

	Stats Analysis			Summary		Individual	
	T	F	L	T	F	F	L
Time to delivery ^[1]	Y		Y	Y	Y		Y
Time to delivery, retreatment or subsequent preterm labor) ^[1]				Y			Y

NOTES :

- T = Table, F = Figure, L = Listing, Y = Yes display generated.
- Stats Analysis = Represents TFL related to any formal statistical analyses (i.e. modelling) conducted.
- Summary = Represents TF related to any summaries (i.e. descriptive statistics) of the observed raw data.
- Individual = Represents FL related to any displays of individual subject observed raw data.

1. Displays generated using the 'ITT' population, with the exception of individual listings.

Following review of the data, additional analyses may be conducted to further support the evaluation and interpretation of the data.

7.1.2. Planned Statistical Analyses

Primary Statistical Analysis
Endpoint

 Time to delivery (days in 1 decimal point) from the start of IP administration until delivery 
The time to delivery is calculated as the days between the delivery and start time of the infusion of IP using the formula below:
 
Time to delivery (days) = date/time of delivery – date/time of start of infusion
 
The exact date/time of delivery and infusion will be used to determine the time to delivery.
 
Time to delivery is a continuous numeric value with one decimal place (e.g. expressed as xx.x days) and the exact date/time of delivery and infusion will be used to determine the time to delivery. For example, if the date/time of delivery was at 00:00 am on 20 March 2015 and date/time of start of infusion was at 12:00 pm on 01 March 2015 APR2015, time to delivery is 19.5 (days).

Model Specification

 The primary endpoint of time to delivery will be statistically analyzed using a two-component finite mixture regression model. Time to delivery (y) is assumed to follow a mixture of two-components with normal densities. Within each component, the expected time to delivery will be modeled as a function of treatment (TRT) as fixed effect, and GA at randomization (GA) and established progesterone use (EP) as covariates., $f(y) = \sum_{k=1}^2 \pi_k(\mathbf{Z}, \alpha_k) N(\mu_k, \sigma_k^2),$ 
where $k = 2$ to denote the 2 groups of mothers namely those who deliver preterm and those who deliver at term.
 
The component normal distributions depend on the regressors: TRT, GA and EP thru the means μ_k, i.e.,
 $\mu_k = \beta_{0k} + \beta_{1k} \cdot \text{trt} + \beta_{2k} \cdot \text{GA} + \beta_{3k} \cdot \text{EP}, \pi_k(\text{trt}, \text{GA}, \text{EP}, \alpha) > 0 \quad \forall k, \sum_{k=1}^2 \pi_k(\text{trt}, \text{GA}, \text{EP}, \alpha) = 1$ 
The mixing probabilities π_k, which are non-negative and sum to one, are modeled using a logistic regression model with TRT, GA and EP and corresponding parameters, α, i.e,
 $\pi_1(\text{trt}, \text{GA}, \text{EP}, \alpha) = \frac{\exp(\alpha_0 + \alpha_1 \cdot \text{trt} + \alpha_2 \cdot \text{GA} + \alpha_3 \cdot \text{EP})}{1 + \exp(\alpha_0 + \alpha_1 \cdot \text{trt} + \alpha_2 \cdot \text{GA} + \alpha_3 \cdot \text{EP})}$ $\pi_2(\text{trt}, \text{GA}, \text{EP}, \alpha) = 1 - \pi_1(\text{trt}, \text{GA}, \text{EP}, \alpha)$ 
The patient assignment of each component is determined by the mixture model described

Primary Statistical Analysis							

above and some patients are pre-assigned to each component to stabilize the model, i.e. the first component includes those deliveries within 1 week of GA at randomization and the second component includes the patients who deliver after 38 weeks of GA.
 
The model parameters can then be estimated using PROC FMM from SAS 9.4 by maximizing the likelihood. Point estimate, associated 95% confidence intervals and p-values for the overall average difference between Retosiban and Atosiban is then derived using weighted average of model parameter estimates and variance from each sub-population of mixture model.
 
 • Additionally, treatment by GA at randomization interaction and treatment by progesterone use interaction will also be investigated. • Terms fitted in the FMM model will include: 
 
 Fixed Categorical:	TRT, EP and their interaction term (TRT*EP). Interaction will be included only if the interaction is statistically significant (at 0.05 level of significance).	
 
 Fixed Continuous Covariates:	GA and interaction term (TRT*GA). Interaction will be included only if both interaction are statistically significant (at 0.05 level of significance).	
 
 Repeated:	None	
 
 		Fixed Categorical:	TRT, EP and their interaction term (TRT*EP). Interaction will be included only if the interaction is statistically significant (at 0.05 level of significance).	Fixed Continuous Covariates:	GA and interaction term (TRT*GA). Interaction will be included only if both interaction are statistically significant (at 0.05 level of significance).	Repeated:	None
Fixed Categorical:	TRT, EP and their interaction term (TRT*EP). Interaction will be included only if the interaction is statistically significant (at 0.05 level of significance).						
Fixed Continuous Covariates:	GA and interaction term (TRT*GA). Interaction will be included only if both interaction are statistically significant (at 0.05 level of significance).						
Repeated:	None						
SAS Code							
<pre>proc fmm data=xxx TECHNIQUE=xxx. partial=xxx ; class TRT EP; model T2D = TRT EP GA TRT*GA TRT*EP/ k=2; probmodel TRT EP GA TRT*GA TRT*EP; run;</pre>							
Model Checking & Diagnostics							

 • Refer to Appendix 9: Model Checking and Diagnostics for Statistical Analyses. 							
Model Results Presentation							

 • Point estimates of the treatment means and standard deviation will be presented, together with the estimate of the treatment mean differences (retosiban – atosiban), the corresponding 95% confidence intervals and p-value. 							
Summary Results Presentation							

 • The following plot of the time to delivery per treatment will be generated. 
 - Kaplan-Meier Plot of Time to Delivery • Observed values using descriptive statistics will be presented for each treatment group. • In addition, time to delivery or retreatment/subsequent preterm labor will be summarized using descriptive statistics. 							

Primary Statistical Analysis
Sensitivity and Support Statistical Analysis

 Time to delivery will be analyzed using an analysis of covariance adjusting for the covariate of GA at randomization and established progesterone use (yes or no). Additionally, interactions between GA at randomization and treatment and established progesterone use and treatment will also be investigated. Observed values using descriptive statistics will be presented within defined subgroups in Section 5.1.

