1.2. Rationale

This study is being conducted based on the results of the OTA10256 study that demonstrated significantly longer time to delivery. Specifically, OTA105256 was a Phase II study of retosiban for the treatment of spontaneous preterm labor in women with singleton pregnancies and intact membranes. This study initially examined the pharmacokinetics, dose response, and safety of retosiban in women for whom the gestational age (GA) was restricted to $34^{0/7}$ and $35^{6/7}$ weeks. Retosiban was given intravenously with the loading dose and infusion rate increased in a stepwise fashion every 3 hours to achieve target plasma concentrations. Alternate tocolytic drugs were not permitted during the study's IV infusion phase. Twenty-nine adult subjects (ages 18 to 37 years) were enrolled into Parts A and B. An interim analysis, indicating retosiban suppressed contractions and prolonged pregnancy, resulted in an additional cohort (Part C with a lowered GA to $30^{0/7}$ weeks) to evaluate retosiban in a clinical population and setting more consistent with current practice guidelines for tocolytic use. Sixty-four adult subjects (ages 18 to 41 years) were enrolled, randomly assigned to treatment, and dosed in Part C.

Data from Study OTA105256 found that retosiban treatment, at a dosing regimen of 6-mg load over 5 minutes, then 6 to 12 mg/hour based on response, was associated with a higher proportion of females achieving uterine quiescence and a significant difference in time to delivery and reduction in preterm births. Uterine quiescence was defined as 4 or fewer contractions per hour with no change in cervical dilation greater than 1 cm. Using partial informative priors, which partially weighted the Part A/B response rates for retosiban and placebo, the posterior mean response rate within the initial 6 hours of treatment was 62% in the retosiban group compared with 41% in the placebo group. The posterior relative risk of achieving quiescence was 1.53 (95% confidence interval [CI]: 0.98, 2.48).

Retosiban treatment was also associated with a significant difference in time to delivery and births prior to 37 weeks of gestation. The posterior mean difference in time to delivery was 8.2 days relative to placebo (95% CI: 2.7, 13.74). The percent of preterm births in the retosiban and placebo groups was 18.7% and 47.2%, respectively. The posterior relative risk for preterm birth in the retosiban group was 0.38 (95% CI: 0.15, 0.81).

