8.2. Study Design Considerations

8.2.1. Sample Size Assumptions

A total of 330 women (165 women per treatment group) will be recruited into the study and randomly assigned to treatment to ensure that 300 women/newborns (150 women/newborns per treatment group, assuming 10% missing data) have recorded

birth data, which provides 86% statistical power to detect an average difference of 9.5 days between retosiban and atosiban in time to delivery in the proposed adaptive design with futility analysis.

The above sample size calculations are based on a 2-sided testing procedure with a type I error rate of 5% and an approximate 10% dropout rate. Calculations are based on simulations and assumes that the percentage of women enrolled into each of the GA strata $24^{0/7}$ to $25^{6/7}$, $26^{0/7}$ to $27^{6/7}$, $28^{0/7}$ to $30^{6/7}$, and $31^{0/7}$ to $33^{6/7}$ will be 7%, 13%, 27%, and 53% (1:2:4:8 ratio), respectively, and approximately 55% of women in the atosiban treatment group will deliver within the 3 weeks of GA at randomization. The details of the model assumption and simulation are included in a supplemental simulation report.

Statistical Operating Characteristics

Simulations were carried out to determine the statistical properties for inference about the primary hypothesis of the adaptive design with regard to the control of the overall type I error and the statistical power under a wide range of efficacy for retosiban, from no effect (i.e., null hypotheses) to an increase of 9.5 days in time to delivery (i.e., alternative hypothesis) and to greater than expected efficacy. It was shown that the overall type I error rate (2.4%) was maintained at a level well below the 5% for the primary hypothesis. Furthermore, if the true effect of retosiban is small or zero, there is good probability (74%) that the study will be stopped early for lack of efficacy (i.e., futility). If the true effect of retosiban is as expected, the statistical power will be 86%, with a 7% probability that the study will be stopped for lack of efficacy. The details of model assumption and simulation are included in a supplemental simulation report.

Table 7 Operating Characteristics of the Adaptive Design Under the Null and Alternative Hypotheses

Case Hypothesis	Interim Analysis		Final	
	Futility	Failure	Failure	Success
Null (0 day)	74%	24%		2.4%
Alternative (9.5 days)	7%	7%		86%

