8.2.2. Sample Size Sensitivity

It is expected that the time to delivery will be dependent on the percentage of women enrolled into each of the GA strata and the percentage of women that deliver within 3 weeks of randomization. Subsequently, the power of the study is expected to be sensitive to the assumptions used to determine the study sample size.

Further work has been done by GSK (details on file with GSK) to evaluate the sensitivity of the power of the study if the assumptions do not hold. In those analyses, the power of the study was most sensitive to assumptions regarding the percentage of women that delivered within 3 weeks of randomization. If the proportion of women delivering within 3 weeks is 45%, 10% lower than expected, the power of the study will be approximately 75% to detect an average difference of 7.7 days between retosiban and atosiban in the time to delivery. If it is significantly lower, such as 20% lower, the power of the study

could be as low as 53% to detect an average difference of 5.8 days between retosiban and atosiban in the time to delivery. Details will be included in a supplemental simulation report.

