8.3.5. Key Elements of Analysis Plan

8.3.5.1. Efficacy Analyses

8.3.5.1.1. Primary Analysis

The primary objective of the statistical analysis will be to test the null hypothesis in the ITT population that there is no difference between retosiban and atosiban in time to delivery versus the alternative hypothesis that there is a difference.

The primary analysis of time to delivery will utilize a finite mixture model [McLachlan, 2000] with 2 components, 1 for those women that delivery imminently and the other for the women delivering at term. The exact weight of each component will be determined by the observations from the component and model concomitant variables including treatment and GA at randomization. Within each component, the expected time to delivery will be modeled as a function of treatment as fixed effect and GA at randomization and established progesterone use (yes or no) as a covariate. The model parameters will be estimated using expectation-maximization algorithm. Point estimates, associated 95% CIs, and p-values for the overall average difference in time to delivery between retosiban and atosiban will be derived using the weighted average of model parameter estimates and variance from each subpopulation of mixture model. Details of mathematical model and analysis will be included in the RAP.

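### The SAP's written variance rule for the primary contrast leaves out the sampling uncertainty of the estimated mixing share

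*SAP*

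**What the plan says.** SAP 7.1.2 models time to delivery as a mixture of two normal components. Treatment, gestational age (GA) and progesterone use enter each component mean. The mixing probabilities "are modeled using a logistic regression model with TRT, GA and EP and corresponding parameters", so the share of women in each component also depends on treatment and is estimated.

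The overall difference, its 95% CI and its p-value are covered by one clause: the result "is then derived using weighted average of model parameter estimates and variance from each sub-population of mixture model". Protocol 8.3.5.1.1 has the same rule ("derived using the weighted average of model parameter estimates and variance from each subpopulation of mixture model") and leaves the mathematics to the RAP. The RAP repeats the clause. It gives no weights for the variance, no variance formula and no use of the covariance between share and mean parameters. The sample SAS code stops at the model fit.

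Three places indicate the intended estimate. The SAP synopsis and protocol 8.3.5.1.1 let the component weights depend on treatment. The synopsis also compares the treatments through mean estimates. The results paragraph of SAP 7.1.2 says: "Point estimates of the treatment means and standard deviation will be presented, together with the estimate of the treatment mean differences". Together these describe Σk πk·μk computed for each arm, and then the difference between arms.

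**The concern.** An arm mean of the form π1·μ1 + π2·μ2 is uncertain for two reasons: the component means are estimated, and so is the share. Averaging component variances deals only with the first. If the components lie far apart, the second is the larger part, because moving a few women from one component to the other shifts the arm mean by many days.

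The clause produces the primary CI and the test at the two-sided 5% level (SAP 2.4). If it is programmed as written around the correct estimate, the CI can be too narrow and the test can reject a true null too often. Stopping at 97 women does not remove this: SAP 7.1.1 and 7.1.2 still plan the test, and the ratio of the written SE to the true SE hardly depends on n.

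**Working it through.** **1. Reproduce the plan's figures.** Inputs from protocol 8.2.1 and Table 7: futility stop 74% under the null and 7% under the alternative; success 2.4% and 86%; effect 9.5 days; 300 evaluable women. Protocol 8.3.4: interim at 130. No SD is stated, so I treat the interim and final statistics as bivariate normal with information fraction 130/300.

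- Futility cut: z = 0.643 (74% below it under the null).
- Interim mean under the alternative: 0.643 + 1.476 = 2.119.
- Final drift: 2.119/√(130/300) = 3.219.
- Implied SE: 9.5/3.219 = 2.95 days.

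The success entries are a separate check. With an SE of the correct size, power is 86.1% (stated 86%) and null success 2.2% (stated 2.4%). Solving for the ratio of SE used to true SE gives 0.98 from the 2.4% and 1.00 from the 86%, or 0.93 to 1.07 allowing for rounding.

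**2. The missing term.** For one arm of n/2 women, the derivative of π1·μ1 + π2·μ2 with respect to π1 is the gap μ1 − μ2, and Var(π1) is about π1·π2/(n/2). Over two arms the share contributes (4/n)·π1·π2·gap². With a common component variance s², and covariates ignored:

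- Full variance: (4/n)·(s² + π1·π2·gap²).
- Plain weights, Σ πk·Var(β1k) with Var(β1k) = 4s²/(n·πk): 8s²/n.
- Squared weights, Σ πk²·Var(β1k): 4s²/n.

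The clause does not say which weighting is meant. Neither contains the gap. Plain weights double the within-component part, which can offset the omission when s² is large.

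**3. Anchor on Table 7.** Full variance: 2.951² × 300/4 = 653. Take π1 = 0.55 (protocol 8.2.1 gives 55% of atosiban women delivering within 3 weeks; treating this as the component share is an assumption). Then π1·π2 = 0.2475 and s² = 653 − 0.2475·gap². Type I error is two-sided at nominal 5%, with no futility stop.

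| Gap (days) | 0.2475·gap² | s² | SE ratio, plain | Type I, plain | SE ratio, squared | Type I, squared |
|---|---|---|---|---|---|---|
| 35 | 303 | 350 | 1.04 | 4% | 0.73 | 15% |
| 40 | 396 | 257 | 0.89 | 8% | 0.63 | 22% |
| 45 | 501 | 152 | 0.68 | 18% | 0.48 | 34% |
| 50 | 619 | 34 | 0.32 | 52% | 0.23 | 65% |

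For orientation on the gap: the SAP pre-assigns women who deliver within 1 week to one component and those who deliver after 38 weeks to the other. With the 1:2:4:8 GA mix and approximate stratum midpoints, mean entry GA is (25 + 2×27 + 4×29.5 + 8×32.5)/15 = 30.5 weeks, so the cuts lie about (38 − 30.47)×7 − 7 = 46 days apart. That is a distance between cut-points, not between component means.

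**4. Simulation of the SAP model.** The mixture was fitted by maximum likelihood with the SAP's pre-assignment, 4,000 null trials per setting and sample size. Component values, a 55% component share and 15% progesterone use are assumed. Null rejection of the difference in arm means:

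| SD early/term (days) | Gap | n=300 plain | n=300 squared | n=97 plain | n=97 squared |
|---|---|---|---|---|---|
| 6/8 | 51 | 47% | 63% | 48% | 63% |
| 6/10 | 47 | 36% | 52% | 38% | 55% |
| 8/14 | 41 | 17% | 34% | 19% | 38% |
| 12/18 | 39 | 8% | 23% | 9% | 25% |
| 15/22 | 32 | 4% | 15% | 5% | 17% |

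With the delta-method SE from the full covariance matrix, the same contrast rejected 5.2–5.7% at n=300 and 5.8–5.9% at n=97. A second simulation with other components (gaps 39 to 54 days) gave 8–59% at n=300 with plain weights. Its base case gave a full-covariance SE of 2.87 days against an empirical SD of 2.87.

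**The case against.** The strongest reply is that the clause is shorthand. It does not forbid a fuller calculation, and the arm-level SD promised in the results paragraph could include the share term. Table 7, the only check anchored in the documents, fits a correctly sized SE. The one version of the written rule in step 3 that also fits it (plain weights, 35-day gap) has 4% type I error. The other versions would give null success of 3.4% to 17.5%, against the stated 2.4%. All component values are assumed. ANCOVA is already planned as a supporting analysis (Table 2.04) and kept its size in simulation (4.9–5.7%).

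Much of this stands. A reader might infer that the sponsor's program has an inflated error rate. The documents do not show that: Table 7 suggests that a fuller variance was simulated, and the supplemental simulation report is not available here. What does not stand is that the clause is merely brief. It is the only variance rule given, in the document that was to supply the mathematics.

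A reader might also infer that the primary analysis would miss a drug that works by moving women from one component to the other. That requires averaging the within-component treatment coefficients with the same weights in both arms. A share-only effect of 9.5 days would then be estimated at −0.1 to 0.1 days at n=300. Treatment-dependent weights and a reported difference in treatment means make this the less supported reading. Nor does Phase II settle how the drug acts. It reported: "The percent of preterm births in the retosiban and placebo groups was 18.7% and 47.2%, respectively". That comparison was with placebo, and the first component is described as imminent delivery in the protocol but as preterm delivery in SAP 7.1.2. The planning effects of 9.5, 7.7 and 5.8 days at early shares of 55%, 45% and 35% come to 17.3, 17.1 and 16.6 days per early woman. This fits a change in share, but also a fixed delay among early deliverers.

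**Conclusion.** The concern holds for the written rule. For a difference in arm means with treatment-dependent shares, a component-averaged variance omits the share's sampling uncertainty. The SE is then too small in most of the settings tried, by an amount the documents cannot fix. The table anchored on Table 7 rests on a normal approximation, a 55% component share and equal SDs. The direction can reverse slightly with plain weights and wide components. Confidence is medium, because the weighting is unstated and the gap unknown.

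The clause should be corrected whichever way the program was written. If the program uses the full covariance, the SAP does not describe it and the primary p-value cannot be reproduced from the plan. If it follows the clause, the p-value may be wrong.

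**What to change.** Before unblinding, replace the clause in SAP 7.1.2 with:

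> Delta = average over all Maternal ITT subjects of Σk πk·μk with treatment set to retosiban, minus the same average with treatment set to atosiban. Its SE is obtained by the delta method from the full joint covariance matrix of the mixing and component-mean parameters. An arm-stratified bootstrap SE is a sensitivity analysis.

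This also rules out the common-weight reading. The planned ANCOVA needs no change.

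The cost is SAP wording and a few lines of code, with no new data. The CI will usually be wider: in the five settings at n=97, the median SE is 4.7–5.2 days, against 1.9–5.0 with plain and 1.3–3.4 with squared component weights. Power for 9.5 days at n=97 is only about 45–53%. Slight inflation, to about 6%, remains with the delta method at that size. The bootstrap SE rejected 4.5–6.0% in the three settings checked.
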